#### **8.1.10 Discontinuation and Withdrawal**

Participants who discontinue study intervention prior to completion of the predefined treatment period for any reason at any time can restart the study intervention. However, participants are expected to rechallenge the study intervention at the earliest time upon decision of the investigator, and all premature discontinued participants should be encouraged to continue to be followed for all remaining study visits, regardless of the rechallenge, as outlined in the SoA and Section 8.11.3.

When a participant withdraws from participation in the study, all applicable activities scheduled for the end of study visit should be performed (at the time of withdrawal). Any AEs that are present at the time of withdrawal should be followed in accordance with the safety requirements outlined in Section 8.4 and 8.11.

### 8.1.11 Participant Blinding/Unblinding

STUDY INTERVENTION IDENTIFICATION INFORMATION IS TO BE UNMASKED ONLY IF NECESSARY FOR THE WELFARE OF THE PARTICIPANT. EVERY EFFORT SHOULD BE MADE NOT TO UNBLIND.

For emergency situations where the investigator or medically qualified designee (consistent with local requirements) needs to identify the intervention used by a participant and/or the dosage administered, he/she will contact the emergency unblinding call center by telephone and make a request for emergency unblinding. As requested by the investigator or medically qualified designee, the emergency unblinding call center will provide the information to him/her promptly and report unblinding to the Sponsor. Prior to contacting the emergency unblinding call center to request unblinding of a participant's intervention assignment, the investigator who is a qualified physician should make reasonable attempts to enter the intensity of the AEs observed, the relation to study intervention, the reason thereof, etc., in the medical chart. If it is not possible to record this assessment in the chart prior to the unblinding, the unblinding should not be delayed.

In the event that unblinding has occurred, the circumstances around the unblinding (eg, date, reason, and person performing the unblinding) must be documented promptly, and the Sponsor Clinical Director notified as soon as possible. Once an emergency unblinding that is part of the study design has taken place, the principal investigator, site personnel, and Sponsor personnel may be unblinded so that the appropriate follow-up medical care can be provided to the participant.

Participants will remain blind to the identity of the treatment from Visit 4 until database lock, using the following methods:

- Randomization data are kept strictly confidential until the time of unblinding, and will not be accessible by anyone involved in the study;
- The identity of the treatment will be concealed by using the identical packaging, labeling, appearance, taste and color. And a double-dummy design is used because differences between investigational treatment and comparator cannot be disguised due to their different appearance;
- Lipid panel test after randomization will be done centrally and the result will not reveal to the participants or study team until end of the study. No attempts could be made to have local evaluation of the lipid levels once the participant successfully entered the double blind treatment phase.

### **8.1.12 Calibration of Equipment**

The investigator or qualified designee has the responsibility to ensure that any device or instrument used for a clinical evaluation/test during a clinical study that provides information about inclusion/exclusion criteria and/or safety or efficacy parameters shall be suitably calibrated and/or maintained to ensure that the data obtained is reliable and/or reproducible. Documentation of equipment calibration must be retained as source documentation at the study site.

## **8.2 Efficacy Assessments**

### **8.2.1 Clinical Efficacy Laboratory Assessments**

Fasting blood samples (obtained at least 10 hours after intake of last meal/food/beverage other than water) will be drawn as outlined in the SoA. The central laboratory will perform all laboratory test determinations from Visit 3 till Visit 6 (Appendix 2). LDL-C will be calculated using the Friedewald method when  $TG \leq 400$  mg/dL and beta quantification ultracentrifugation when  $TG > 400$  mg/dL. All Lipid Panel A and Apo B data will be blinded once the participant is centrally randomized. Once a participant is randomized (Visit 4), no attempts should be made on the part of the investigator or participant to have a local evaluation of the participant's lipid values (Lipid Panel A and Apo B).

## **8.3 Safety Assessments**

The assessment of safety will be based primarily on the frequency of AEs, SAEs, and laboratory abnormalities. Other safety data will be summarized as appropriate.

1. Laboratory evaluations (performed at baseline and at the end of the study)
2. Adverse events and serious adverse events, adverse events of interest including muscular event and hepatic events (performed throughout full study)
3. Discontinuation due to AEs (performed throughout full study)
4. Physical Exam (performed throughout full study)
5. Vital signs (performed throughout full study)

Details regarding specific safety procedures/assessments to be performed in this study are provided. The total amount of blood/tissue to be drawn/collected over the course of the study (from prestudy to poststudy visits), including approximate blood/tissue volumes drawn/collected by visit and by sample type per participant, can be found in Section 8.

Planned time points for all safety assessments are provided in the SoA.

### **8.3.1 Physical Examinations**

A complete physical examination will be conducted by an investigator or medically qualified designee (consistent with local requirements) as per institutional standard at screening and scheduled timepoint.

Height and weight will also be measured and recorded. Body height and weight will be obtained with the participants shoes off, jacket or coat removed, using a standardized scale.

The investigator will determine if the results are clinically significant prior to Week 0 (Visit 4), any physical examination abnormalities will be recorded as part of the participant's medical history. Investigators should pay special attention to clinical signs related to previous serious illnesses.

### **8.3.2 Vital Signs**

- Heart rate and blood pressure will be assessed.
- Blood pressure and pulse measurements will be assessed in sitting position with a completely automated device. Manual techniques will be used only if an automated device is not available.
- Blood pressure and pulse measurements should be preceded by at least 5 minutes of rest for the participant in a quiet setting without distractions.
- Vital signs (to be taken before blood collection for laboratory tests, or at least 5 minutes afterwards) will consist of 1 pulse and 3 blood pressure measurements (after the participant has been sitting for 5 minutes, 3 consecutive blood pressure readings will be recorded at intervals of at least 1 minute).
- Any clinically significant change from baseline for vital sign measurement (not associated with another adverse event) will be recorded.

### **8.3.3 Electrocardiograms**

- 12-lead electrocardiogram (ECG) will be obtained and reviewed by an investigator or medically qualified designee (consistent with local requirements) as outlined in the SoA using an ECG machine that automatically calculates the heart rate and measures PR, QRS, QT, and QTc intervals.
- The investigator will determine if the results are clinically significant and they meet the eligibility criteria. Any ECG abnormalities at screening visit will be recorded as part of the participant's medical history.

### 8.3.4 Clinical Safety Laboratory Assessments

Refer to Appendix 2 for the list of clinical laboratory tests to be performed and to the SoA for the timing and frequency.

- The investigator or medically qualified designee (consistent with local requirements) must review the laboratory report, document this review, and record any clinically relevant changes occurring during the study in the AE section of the case report form (CRF). The laboratory reports must be filed with the source documents. Clinically significant abnormal laboratory findings are those which are not associated with the underlying disease, unless judged by the investigator to be more severe than expected for the participant's condition.
- All protocol-required laboratory assessments, as defined in Appendix 2, must be conducted in accordance with the laboratory manual and the SoA.
- If laboratory values from nonprotocol specified laboratory assessments performed at the institution's local laboratory require a change in study participant management or are considered clinically significant by the investigator (eg, SAE or AE or dose modification), then the results must be recorded in the appropriate CRF (eg, SLAB).
- For any laboratory tests with values considered clinically significantly abnormal during participation in the study or within 14 days after the last dose of study intervention, every attempt should be made to perform repeat assessments until the values return to normal or baseline or if a new baseline is established as determined by the investigator.

### 8.4 Adverse Events (AEs), Serious Adverse Events (SAEs), and Other Reportable Safety Events

The definitions of an AE or SAE, as well as the method of recording, evaluating, and assessing causality of AE and SAE and the procedures for completing and transmitting AE, SAE, and other reportable safety event reports can be found in Appendix 3.

Adverse events, SAEs, and other reportable safety events will be reported by the participant (or, when appropriate, by a caregiver, surrogate, or the participant's legally authorized representative).

The investigator and any designees are responsible for detecting, documenting, and reporting events that meet the definition of an AE or SAE as well as other reportable safety events. Investigators remain responsible for following up AEs, SAEs, and other reportable safety events for outcome according to Section 8.4.3.

The investigator, who is a qualified physician, will assess events that meet the definition of an AE or SAE as well as other reportable safety events with respect to seriousness, intensity/toxicity and causality.

#### **8.4.1 Time Period and Frequency for Collecting AE, SAE, and Other Reportable Safety Event Information**

All AEs, SAEs, and other reportable safety events that occur after the consent form is signed but before intervention allocation/randomization must be reported by the investigator if the participant is receiving placebo run-in or other run-in treatment, if the event causes the participant to be excluded from the study, or is the result of a protocol-specified intervention, including but not limited to washout or discontinuation of usual therapy, diet, or a procedure.

From the time of intervention allocation/randomization through 14 days following cessation of treatment, all AEs, SAEs, and other reportable safety events must be reported by the investigator.

Additionally, any SAE brought to the attention of an investigator at any time outside of the time period specified in the previous paragraph must be reported immediately to the Sponsor if the event is considered related to study intervention.

Investigators are not obligated to actively seek AEs or SAEs or other reportable safety events in former study participants. However, if the investigator learns of any SAE, including a death, at any time after a participant has been discharged from the study, and he/she considers the event to be reasonably related to the study intervention or study participation, the investigator must promptly notify the Sponsor.

All initial and follow-up AEs, SAEs, and other reportable safety events will be recorded and reported to the Sponsor or designee within the time frames as indicated in [Table 5](#).

Table 5 Reporting Time Periods and Time Frames for Adverse Events and Other Reportable Safety Events

Type of Event	Reporting Time Period: Consent to Randomization/ Allocation	Reporting Time Period: Randomization/ Allocation through Protocol-specified Follow-up Period	Reporting Time Period: After the Protocol-specified Follow-up Period	Time Frame to Report Event and Follow-up Information to Sponsor:
Nonserious Adverse Event (NSAE)	Report if: - due to protocol-specified intervention - causes exclusion - participant is receiving placebo run-in or other run-in treatment	Report all	Not required	Per data entry guidelines

Type of Event	Reporting Time Period: Consent to Randomization/Allocation	Reporting Time Period: Randomization/Allocation through Protocol-specified Follow-up Period	Reporting Time Period: After the Protocol-specified Follow-up Period	Time Frame to Report Event and Follow-up Information to Sponsor:
Serious Adverse Event (SAE)	Report if: - due to protocol-specified intervention - causes exclusion - participant is receiving placebo run-in or other run-in treatment	Report all	Report if: - drug/vaccine related. (Follow ongoing to outcome)	Within 24 hours of learning of event
Pregnancy/Lactation Exposure	Report if: - due to intervention - causes exclusion	Report all	Previously reported – Follow to completion/termination; report outcome	Within 24 hours of learning of event
Event of Clinical Interest (require regulatory reporting)	Report if: - due to intervention - causes exclusion	Report - Potential drug-induced liver injury (DILI) - Require regulatory reporting	Not required	Within 24 hours of learning of event
Event of Clinical Interest (do not require regulatory reporting)	Report if: - due to intervention - causes exclusion	Report - non-DILI ECIs and those not requiring regulatory reporting	Not required	Within 5 calendar days of learning of event
Cancer	Report if: - due to intervention - causes exclusion	Report all	Not required	Within 5 calendar days of learning of event
Overdose	Report if: - receiving placebo run-in or other run-in medication	Report all	Not required	Within 5 calendar days of learning of event

#### 8.4.2 Method of Detecting AEs, SAEs, and Other Reportable Safety Events

Care will be taken not to introduce bias when detecting AEs and/or SAEs and other reportable safety events. Open-ended and nonleading verbal questioning of the participant is the preferred method to inquire about AE occurrence.

#### **8.4.3 Follow-up of AE, SAE, and Other Reportable Safety Event Information**

After the initial AE/SAE report, the investigator is required to proactively follow each participant at subsequent visits/contacts. All AEs, SAEs, and other reportable safety events including pregnancy and exposure during breastfeeding, events of clinical interest (ECIs), cancer, and overdose will be followed until resolution, stabilization, until the event is otherwise explained, or the participant is lost to follow-up (as defined in Section 7.3). In addition, the investigator will make every attempt to follow all nonserious AEs that occur in randomized participants for outcome. Further information on follow-up procedures is given in Appendix 3.

#### **8.4.4 Regulatory Reporting Requirements for SAE**

Prompt notification (within 24 hours) by the investigator to the Sponsor of SAE is essential so that legal obligations and ethical responsibilities towards the safety of participants and the safety of a study intervention under clinical investigation are met.

The Sponsor has a legal responsibility to notify both the local regulatory authority and other regulatory agencies about the safety of a study intervention under clinical investigation. The Sponsor will comply with country-specific regulatory requirements and global laws and regulations relating to safety reporting to regulatory authorities, IRB/IECs, and investigators.

Investigator safety reports must be prepared for suspected unexpected serious adverse reactions (SUSARs) according to local regulatory requirements and Sponsor policy and forwarded to investigators as necessary.

An investigator who receives an investigator safety report describing an SAE or other specific safety information (eg, summary or listing of SAE) from the Sponsor will file it along with the IB and will notify the IRB/IEC, if appropriate according to local requirements.

#### **8.4.5 Pregnancy and Exposure During Breastfeeding**

Although pregnancy and infant exposure during breastfeeding are not considered AEs, any pregnancy or infant exposure during breastfeeding in a participant (spontaneously reported to the investigator or their designee) that occurs during the study are reportable to the Sponsor.

All reported pregnancies must be followed to the completion/termination of the pregnancy. Pregnancy outcomes of spontaneous abortion, missed abortion, benign hydatidiform mole, blighted ovum, fetal death, intrauterine death, miscarriage, and stillbirth must be reported as serious events (Important Medical Events). If the pregnancy continues to term, the outcome (health of infant) must also be reported.

#### **8.4.6 Disease-related Events and/or Disease-related Outcomes Not Qualifying as AEs or SAEs**

Refer to Appendix 3.

#### **8.4.7 Events of Clinical Interest (ECIs)**

Selected nonserious and SAEs are also known as ECIs and must be reported to the Sponsor.

Events of clinical interest for this study include:

1. An elevated AST or ALT lab value that is greater than or equal to 3X the upper limit of normal and an elevated total bilirubin lab value that is greater than or equal to 2X the upper limit of normal and, at the same time, an alkaline phosphatase lab value that is less than 2X the upper limit of normal, as determined by way of protocol-specified laboratory testing or unscheduled laboratory testing.\*

\*Note: These criteria are based upon available regulatory guidance documents. The purpose of the criteria is to specify a threshold of abnormal hepatic tests that may require an additional evaluation for an underlying etiology. The study site guidance for assessment and follow-up of these criteria can be found in the Investigator Study File Binder (or equivalent).

2. An overdose of Sponsor's product, as defined in Section 8.5, that is not associated with clinical symptoms or abnormal laboratory results.
3. Myopathy, rhabdomyolysis, or if the CK criterion necessitating study medication discontinuation is met, the event should be reported as ECI because of their association with lipid-lowering treatments.

#### **8.5 Treatment of Overdose**

In this study, an overdose is any dose higher than the amount of study treatment taken outside the treatment assignment.

Sponsor does not recommend specific treatment for an overdose.

Decisions regarding dose interruptions or modifications will be made by the investigator in consultation with the Sponsor Clinical Director based on the clinical evaluation of the participant.

#### **8.6 Pharmacokinetics**

PK parameters will not be evaluated in this study.

#### **8.7 Pharmacodynamics**

Pharmacodynamic parameters will not be evaluated in this study.

#### **8.8 Future Biomedical Research Sample Collection**

Future biomedical research samples will not be collected in this study.

## **8.9 Planned Genetic Analysis Sample Collection**

Planned genetic analysis samples will not be evaluated in this study.

## **8.10 Biomarkers**

Biomarkers are not evaluated in this study.

## **8.11 Visit Requirements**

Visit requirements are outlined in Section 1.3. Specific procedure-related details are provided in Section 8.

### **8.11.1 Screening (Visit 1)**

Approximately 6-7 weeks prior to intervention allocation/randomization, potential participants will be evaluated up to 2 weeks, to determine that they fulfill the entry requirements as set forth in Section 5. Screening procedures may be repeated after consultation with the Sponsor. A participant may be re-screened up to two times. The participant must provide new written informed consent before each time they are re-screened.

A participant who enters screening but is determined not to be eligible to enter the treatment run-in epoch will be considered a screen failure. The investigator may consider re-screening the participant at a later time if he/she believes that the participant's condition has changed and they may potentially be eligible. In this case, a new participant number will be allocated to the participant and he/she will need to re-perform all Visit 1 procedures.

### **8.11.2 Run-In (Visit 2 and Visit 3)**

Visit 2 will be performed approximately 5 weeks prior to randomization (Visit 4).

Dispense run-in intervention to a participant if he/she is eligible for study participation. Participants will be instructed to take 1 tablet from the bottle.

After initiating administration, participant who is determined to be not appropriate by the investigator will be excluded the study as screen failed. If a participant is not eligible for study participation, the investigator should contact with the participant, stop dosing study drug and performing the end of study visit immediately, and a safety follow-up visit by phone-call as appropriate.

*NOTE: it is not necessary for screen failed participant who did not start the study intervention to perform follow-up visit after the end of study visit.*

Approximately 4 weeks after Visit 2, participants will be scheduled to return for Visit 3. Blood lipid levels (e.g. LDL-C values) and biochemistry test measured at Visit 3 (Week -1) will be used to determine participant's eligibility for intervention allocation/randomization at Visit 4 (Day 1/Week 0).

Participant will be instructed on Chinese Guidelines on Prevention and Treatment of Dyslipidemia in Adults (2016 Edition), and will agree to maintain the diet/exercise regimen throughout the study.

No rescreening will be allowed of participants who discontinue during the run-in phase or fail to be eligible after the run-in phase.

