### **5 STUDY POPULATION**

Male/Female participants between the ages of 18 and 80 years (inclusive) with hypercholesterolemia and inadequately controlled by low to median dose of statins only (see below) will be enrolled in this study.

Prospective approval of protocol deviations to recruitment and enrollment criteria, also known as protocol waivers or exemptions, is not permitted.

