### **Visit 4 Criteria**

9. Participant has completed the 5-week atorvastatin run-in period.
10. Participant has  $\geq 75\%$  compliance with study medication during the atorvastatin run-in period.
11. Participant meets any of the following criteria on LDL-C level based on the lipid panel test at Visit 3.
  - a. For medium or low risk participants:  $\geq 130$  mg/dL (3.4 mmol/L).
  - b. For high risk participants:  $\geq 100$  mg/dL (2.6 mmol/L) and  $\leq 160$  mg/dL (4.1 mmol/L).
  - c. For very high risk participants:  $\geq 70$  mg/dL (1.8 mmol/L) and  $\leq 160$  mg/dL (4.1 mmol/L).

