### 9.6.1 Statistical Methods for Efficacy Analyses

This section describes the statistical methods that address the primary and secondary objectives.

The study's estimand is a hypothetical estimand that seeks to estimate efficacy as if all participants were to take study medication for 12 weeks.

The estimand consists of the following elements:

- Target population: Participants with hypercholesterolemia (age 18 to 80 years, inclusive), consistent with the study's inclusion/exclusion criteria.
- Variable: Percent change from baseline in LDL-C at Week 12.
- Intercurrent event: Data obtained after discontinuation of treatment are not relevant to this estimand.
- Population level-summary: Difference in variable means comparing randomized treatments (within each cohort).

Analyses will thus exclude measurements collected more than 5 days after the last dose of study treatment.

For the analyses of percent change from baseline in LDL-C at Week 12 in both cohorts, a constrained longitudinal data analysis (cLDA) method proposed by Liang and Zeger will be used [Liang, Kung-Yee and Zeger, Scott L. 2000]. Within each baseline disease risk category (i.e., stratum), this model assumes a common mean across treatment groups at baseline and a different mean for each treatment at each of the post-baseline time points. In this model, the response vector consists of baseline and the values (percent change) observed at each post-baseline time point. Time is treated as a categorical variable so that no restriction is imposed on the trajectory of the means over time. The analysis model will adjust for time and the interaction of time by treatment, and time by baseline disease risk category given in Section 4.1. The treatment difference in terms of mean change from baseline to Week 12 will be estimated and tested from this model. An unstructured covariance matrix will be used to model the correlation among repeated measurements.

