The percentage of participants reaching the LDL-C goals will be analyzed via a logistic regression model with LDL-C goal achievement rate as response variable and treatment and baseline disease risk category given in Section 4.1 as explanatory variables. Odds ratio estimate derived from the logistic regression model and 95% CI will be used to quantify the treatment effect. Imputation of missing data will be based on the marginal univariate normal distributions with means equal to the predicted values and variances equal to the squared standard errors for the predicted values from the cLDA model. Ten sets of imputations of each missing value will be constructed from the cLDA model. Odds ratio estimate derived from the logistic regression model and 95% confidence interval will be used to quantify the treatment effect. Other exploratory endpoints will be evaluated using the same cLDA model, but TG will be transformed by the natural logarithm on account of the non-normality of this endpoint. Geometric mean percent changes from baseline in TG will be calculated based on back-transformation via exponentiation of the model-based LS means and expressed as (geometric mean – 1) multiplied by 100. The treatment differences in geometric mean percent changes from baseline will be calculated based on the difference in the back transformed model-based LS means and 95% confidence intervals (CIs) for the differences will be calculated using the delta method [Wong, P., et al 1999]. Key efficacy analysis is summarized in [Table 6](#).

Table 6 Analysis Strategy for Key Efficacy Variables

Endpoint/Variable	Statistical Method	Analysis Population	Missing Data Approach
Primary Hypotheses			
Percent change from baseline in LDL-C at Week 12	cLDA †	FAS	Model-based
† Constrained LDA model with terms for treatment, time, the interaction of time by treatment and time by baseline disease risk category.			

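### The primary model leaves out the central-laboratory Visit 3 LDL-C that entry requires of every randomized participant; adding it as a covariate would be a small, optional gain in precision

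*Combined protocol and SAP*

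**What the plan says.** **Visit 3 value.** Section 5.1, Visit 4 Criteria, item 11 reads "Participant meets any of the following criteria on LDL-C level based on the lipid panel test at Visit 3", with LDL-C limits that depend on risk category. Section 5 says that advance approval of departures from the entry criteria, "also known as protocol waivers or exemptions, is not permitted". Section 8.11.2 names "Blood lipid levels (e.g. LDL-C values) and biochemistry test measured at Visit 3" and states their purpose: the values "measured at Visit 3 (Week -1) will be used to determine participant's eligibility for intervention allocation/randomization at Visit 4". The schedule in Section 1.3 requires at least 10 hours of fasting and places Visit 3 at Week -1. By then participants have taken the run-in dose for about four weeks. Section 8.2.1 says "The central laboratory will perform all laboratory test determinations from Visit 3 till Visit 6", so Visits 3 and 4 share a laboratory.

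**Primary model.** Section 9.6.1 says "the response vector consists of baseline and the values (percent change) observed at each post-baseline time point". The schedule labels Visit 4 as baseline. The Table 6 footnote lists the terms: "Constrained LDA model with terms for treatment, time, the interaction of time by treatment and time by baseline disease risk category". Visit 3 LDL-C is neither a response nor a covariate. Further model details are left to the supplemental SAP, but this term list is already fixed in the protocol.

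**What the model already does.** The baseline LDL-C is in the response vector with an unstructured covariance. Section 9.6.1 adds that, with no missing data, the treatment difference equals that of a longitudinal ANCOVA with baseline as covariate.

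**The concern.** The percent change divides by one LDL-C reading, so day-to-day and assay variation in the Visit 4 value enters the endpoint. Adjusting for Visit 4 removes part of that noise, but one reading cannot separate a participant's true run-in level from its error. Visit 3 is a second reading of the same quantity about a week earlier. Unless Visit 4 is free of error, Visit 3 helps to predict the Week 12 percent change after Visit 4 has been accounted for.

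Using it cannot bias the comparison. It precedes randomization, and the selection on it applies equally to both arms. At stake is a slightly narrower confidence interval in each cohort. The planned figure with most room to improve is the 88% power to succeed on both hypotheses.

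**Working it through.** **Inputs (Section 9.9).** 81 and 121 evaluable participants per arm; differences of 12.3 and 10.5 points; unconditional SDs of 22 and 23; one-sided alpha 0.025.

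**Step 1: reproduce the plan's power.** Power = Φ(δ / (SD·√(2/n)) − 1.96).
- Cohort A: 12.3 / (22·√(2/81)) = 3.558, so Φ(1.598) = 94.5%. The plan states 93%.
- Cohort B: 10.5 / (23·√(2/121)) = 3.551, so Φ(1.591) = 94.4%. The plan states 95%.
- Half-widths, 1.96·SD·√(2/n): 6.78 and 5.80. The plan states 7.0 and 5.7.

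The powers agree to within two points. A common SD of about 22.6 fits the stated figures more closely: with the t distribution it gives 93.1% and 94.9%, and half-widths of 7.0 and 5.7. Both bases are used below, and the choice hardly matters here.

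**Step 2: effect of adding Visit 3.** Let r be the partial correlation of Visit 3 LDL-C with Week 12 percent change, given Visit 4 LDL-C and risk category. Residual variance is multiplied by R = 1 − r². The documents do not give r, nor the within-person CV from which it could be derived.

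**Step 3: plausible r (assumptions, not document figures).** A simulation used log-normal true LDL-C, a between-person SD of log LDL-C of 0.15 or 0.25, and a within-person SD of 0.06 to 0.14, independent across visits. The three risk-specific Visit 3 limits of criterion 11 were applied. Individual variation in response was tuned so that the SD of percent change, allowing for risk category only, was about 22.5. The first three result columns are residual SDs of the Week 12 percent change.

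| Within / between SD | Risk only | + Visit 4 | + Visits 4 and 3 | R | r |
|---|---|---|---|---|---|
| 0.06 / 0.15 | 22.57 | 22.46 | 22.27 | 0.983 | 0.13 |
| 0.10 / 0.15 | 22.44 | 21.85 | 21.51 | 0.969 | 0.18 |
| 0.10 / 0.25 | 22.43 | 22.06 | 21.60 | 0.959 | 0.20 |
| 0.14 / 0.15 | 22.39 | 20.76 | 20.37 | 0.963 | 0.19 |
| 0.14 / 0.25 | 22.50 | 21.38 | 20.77 | 0.944 | 0.24 |

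Visit 3 therefore removes about 2-6% of the residual variance. A further simulation, with a single 70-160 mg/dL window and CVs of 6%, 10% and 15%, gave R of about 0.975, 0.945 and 0.91-0.92. The last corresponds to an 8-9% reduction.

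**Step 4: convert to power.** Power = Φ(z/√R − 1.96), with z from Step 1 (3.464 and 3.614 when the SD is 22.6).
- R = 0.983: A 94.5% to 94.8%, B 94.4% to 94.8%. With SD 22.6: A 93.4% to 93.7%, B 95.1% to 95.4%.
- R = 0.944: A 94.5% to 95.6%, B 94.4% to 95.5%. With SD 22.6: A 93.4% to 94.6%, B 95.1% to 96.1%.
- Gain per cohort: about 0.3 to 1.2 points.
- Half-widths from R = 0.983 to 0.944: A 6.78 falls to 6.72-6.58; B 5.80 falls to 5.75-5.63.
- Power for both hypotheses (product of the two, t distribution, SDs 22 and 23): 88.8% rises to 89.2% at r = 0.1 and 90.3% at r = 0.2.

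**Step 5: check the SD used.** Step 4 treats 22 and 23 as if they were already adjusted for Visit 4, but the plan calls them unconditional. Putting the table's adjusted SDs straight into the Cohort A formula gives 93.6% to 94.0% in the first row (22.46 to 22.27) and 95.6% to 96.5% in the last (21.38 to 20.77). The gains are 0.4 and 0.9 points, inside the range above. At a CV of 15% the Visit-4-adjusted SD is already about 20. Cohort A power is then 12.3 / (20·√(2/81)) = 3.914, Φ(1.954) = 97.5% without Visit 3, and with R = 0.92 it is 98.3%, a gain of 0.8 points. A large cut in variance at high CV therefore does not bring a correspondingly large gain in power.

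**The case against.** The strongest reply is that nothing in the plan is wrong. The model is valid, it already adjusts for baseline LDL-C, and stated power is 93%, 95%, 99% for at least one hypothesis and 88% for both. About one power point will rarely change a conclusion. All of this stands, and it is why the point is optional.

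The gain also rests on an assumed within-person CV. The simulation treats errors at Visits 3 and 4 as independent, although the visit windows allow the two draws to be only 1 to 10 days apart. Short-term correlation between them would shrink the gain. That stands too.

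Four stronger readings are tempting, and the documents do not support them.
- *All the Visit 4 noise reaches the treatment comparison.* It does not; Section 9.6.1 already regresses part of it out.
- *The gain is about 1.5 points at high CV (94.5% to 96.0% in Cohort A).* That comes from using the unconditional SD as though it were the Visit-4-adjusted one. Step 5 gives about 0.8. A CV of 15% is also hard to reconcile with a total SD of 22, because it leaves little room for true differences in response.
- *Visit 3 may equally well enter as an extra response or as a covariate.* The two are close but not the same. Criterion 11 truncates Visit 3 at limits that differ by risk category, and a single common normal covariance fits such a variable poorly.
- *The change is free.* It needs no data, but Section 9 requires a protocol amendment for changes to methods tied to the hypotheses, and the Code of Conduct in Appendix 1 calls for ethics approval of significant changes.

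**Conclusion.** The point holds as an optional efficiency gain. A second pre-randomization LDL-C is required of every randomized participant, and the primary model does not use it. Including it would leave the treatment comparison unbiased and could only help precision or leave it essentially unchanged.

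The likely size is 2-6% less residual variance, and up to 8-9% at the least plausible upper end. That is roughly 0.3-1.2 power points per cohort. These figures depend on an assumed within-person CV of 6-15% and on independent errors at the two visits; the documents supply neither. If r were zero, the loss would be about one degree of freedom per time point. The plan is neither biased nor underpowered for lack of Visit 3.

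**What to change.** Before unblinding, amend Section 9.6.1 and the Table 6 footnote to add Visit 3 LDL-C as a covariate with its own coefficient at each time point (time by Visit 3 LDL-C). The covariate form is preferred to an extra response because it makes no distributional assumption about a value truncated by the entry limits. State in the same place that Visit 4 remains the baseline for percent change, so the endpoint and estimand do not change. Also state how a Visit 3 value missing through a protocol deviation will be handled, so that the covariate does not drop anyone from the full analysis set.

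The cost is about one degree of freedom per time point and a few lines in a protocol amendment, with no new samples, visits or participants. The gain hardly justifies an amendment of its own, so the change is best carried with another one made before unblinding. If the sponsor prefers to leave the primary model alone, the same model can be prespecified in the supplemental SAP as a supportive analysis.
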